9.4 Serious Adverse Event Reporting

All SAEs at least possibly related to study treatment will be considered unexpected and be reported as SUSARs within the regulatory timelines outlined in [Table 21](https://www.fda.gov/drugs/investigational-new-drug-ind-application/ind-application-reporting-safety-reports).

All SAEs at least possibly related to study treatment occurring during the study must be reported to the UNC IRB per the UNC IRB reporting requirements. A written report will be submitted to the FDA as outlined in [Table 21](#). Additional information will be supplied as requested.

All SAEs occurring during the study will be reported to DAIDS as outlined in [Table 21](#).

All SAEs considered possibly related to study product must be followed until recovery to baseline or stabilization with the date of resolution or stabilization recorded in the source documents. In addition, the investigator should report all follow-up for reportable SAEs to the UNC IRB. Resolution of an event is defined as the return to pre-treatment status or stabilization of the condition with the expectation that it will remain chronic.

All SAEs determined as possibly related to the vaccine/placebo that have not resolved by the end of the study, or that have not resolved upon discontinuation of the participant's participation in the study, must be followed until any of the following occurs:

1. The event resolves.
2. The event stabilizes.
3. The event returns to baseline, if a baseline value/status is available.
4. The event can be attributed to etiology other than the vaccine/placebo or to factors unrelated to study conduct.
5. It becomes unlikely that any additional information can be obtained (participant's or health care practitioner's refusal to provide additional information, or lost to follow-up after demonstration of due diligence with follow-up efforts)

Any event requiring hospitalization (or prolongation of hospitalization) that occurs during the course of a participant's participation in a study must be reported as an SAE, except hospitalizations for the following:

1. Hospitalizations not intended to treat an acute illness or adverse event (e.g., social reasons such as pending placement in long-term facility)
2. Surgery or procedure planned before entry into the study (must be documented in the source document)

The protocol PI (or designee) will be responsible for notifying the UNC IRB, FDA, the University of Oxford, and DAIDS of any unexpected fatal or life-threatening SAEs as soon as possible, but in no case later than the timelines described in [Table 21](#). In addition, the PI must notify the FDA in an IND safety report of potential serious risks, from clinical trials or any other source, as soon as possible, but in no case later than 15 calendar days after the sponsor determines that the information qualifies for reporting.

9.5 AESI reporting

If an AESI occurs, the study coordinator, in collaboration with the site PI or designee, will evaluate the severity and seriousness of the AE and the relationship to the study treatment, and will document the findings. The protocol team should be contacted within 24 hours of notification of any AESIs (reference Section [8.3.4](#)).

All AESIs occurring during the study must be reported to the UNC IRB per the UNC IRB reporting requirements. **A written report will be submitted to the DAIDS MO and the IRB within 24 hours of site becoming aware of the AESI.** Additional information will be supplied as requested.

All AESIs, serious and non-serious, must be reported using the same reporting process as for SAE reporting.

9.6 Other Reporting Situations

9.6.1 *Reporting to DAIDS*

The Protocol Team will be responsible for reporting to DAIDS the following information via email to [contact].

- a. Monthly listing of all AEs within 5 business days of the 1st of each month.
- b. Monthly Line listing of SAEs including suspected unexpected serious adverse reactions (SUSARs) within 5 business days of the 1st of each month.
- c. All safety reports submitted to the FDA within 48 hours of submission.
- d. All IND submissions within 5 business days of submission.
- e. All FDA communications within 5 business days of the communication.
- f. Notification that the study is halted or put on clinical hold by the PI, IRB, FDA or other regulatory entity within 24 hours of notification that the study was halted or put on hold.
- g. All annual reports to FDA within 5 business days of the submission.
- h. Open SMC or DSMC summary reports within 5 business days of open report finalization.

9.6.2 *Reporting Events to Participants*

We are engaged in a number of similar studies of novel immunotherapies for HIV, persistent HIV infection, monoclonal antibodies, latency reversing agents, and other interventions. We report the scientific findings of our work in the literature and have regular (annual or more frequent) presentations with the local and national HIV-infected and affected community. Due to

the lack of evidence thus far that our studies have a clinical impact, we discuss the scientific findings in a general way with each participant after EOS visits. Our studies have extremely stringent stopping criteria, and thus far, we have had no relevant or study-related SAEs to report. We would inform all study participants by letter or electronic messaging of any AEs determined by the External Study SMC to merit such notice.

9.6.3 *Reporting of Pregnancy*

If the participant becomes pregnant during the study, vaccine/placebo will not be administered. Although not considered an adverse experience, it is the responsibility of investigators or their designees to report any pregnancy in a participant or participant's partner (spontaneously reported to them) that occurs during the study or within 4 months after vaccination. All participants or their partners who become pregnant must be followed to the completion/termination of the pregnancy. If the pregnancy continues to term, the outcome (health of infant) must also be reported to the UNC IRB, the DAIDS Medical Officer, and the FDA (US Food and Drug Administration).

If a male participant impregnates his partner while he is participating in this study, the pregnancy must be reported and the study PI (or designee) should make a concerted effort to follow the pregnancy and outcome. The study PI (or designee) will make every effort to obtain a medical release and a separate pregnancy outcome consent from the pregnant partner granting permission to follow the health of both the pregnant partner and her unborn child to the UNC IRB, DAIDS, study product sponsor, and FDA without delay and within 24 hours if the outcome is an SAE (e.g. death, abortion, congenital anomaly, or other disabling or life-threatening complication to the mother or newborn).

Pregnancy and pregnancy outcome will be recorded. Pregnancies that occur on study should be reported prospectively to the Antiretroviral Pregnancy Registry. More information is available at www.apregistry.com. [contact]; [contact].

9.6.4 *Pregnancy Outcomes and Reporting*

If a woman has completed the study or chooses to discontinue from the study before the end of the pregnancy, then site study staff should request permission via a separate pregnancy outcome consent to contact her regarding pregnancy outcomes at the end of pregnancy. If the information is obtained, pregnancy outcomes will be submitted at the end of the pregnancy.

Pregnant women will discontinue study treatment and will be encouraged to continue on study and complete the evaluations included in the post-treatment evaluation section. At the end of the pregnancy, outcome and adverse events for participant and infant will be recorded. If pregnancy is suspected in a woman on study after study treatment, then a pregnancy test should be obtained. If pregnancy is confirmed, then further study treatment will be discontinued and the woman should continue on study (off study product) safety follow-up visits as noted in the SOE. Stored plasma/PBMC for stored plasma for virologic studies should not be obtained to minimize blood volume.

The site study staff should request permission via a separate pregnancy outcome consent to contact her regarding pregnancy outcomes at the end of pregnancy. A visit 6 months following the end of pregnancy will be conducted to assess for evidence of adverse events (AEs) in the participant and infant and documented.

9.6.5 *Product Quality*

Any suspected transmission of an infectious agent via a medicinal product or other product quality issue that results in an event of clinical consequence are AEs. The product quality issue must be reported within 1 business days after being made aware of the event.

A product quality complaint (PQC) is any written, electronic or oral communication that states possible deficiencies of a study product related to manufacturing, labeling, or packaging, i.e., any dissatisfaction relative to the identity, quality, durability, or reliability of a product, including its labeling or package integrity. A PQC may have an impact on the safety and efficacy of the product. Timely, accurate, and complete reporting and analysis of PQC information from studies is crucial for investigators, the manufacturer and IND sponsor UNC, and for the protection of the participants' rights, welfare and well-being; and is mandated by regulatory agencies worldwide. UNC has established procedures in conformity with regulatory requirements to ensure appropriate reporting of PQC information and all trials will be conducted in accordance with those procedures.

All initial PQCs must be reported to DAIDS by the study-site personnel within 1 business day after being made aware of the event.

If the complaint is combined with an SAE, the study-site personnel must report the PQC to DAIDS the sponsor according to the SAE reporting timelines (refer to Section 9.4, SAEs). A sample of the suspected product should be maintained under correct storage conditions for further investigation if requested by DAIDS.

UNC must report any self-identified or site personnel-reported PQC to DAIDS within one business days of being made aware of the complaint and include notifications regarding immediate action taken.

9.7 *New Safety Information*

9.7.1 *Definition of New Safety Information (NSI)*

The Office for Human Research Protections (OHRP) considers new safety Information involving risks to participants or others as NSI and this includes, in general, any incident, experience, or outcome that meets all of the following criteria:

1. Unexpected in terms of nature, severity, or frequency given (a) the research procedures/study treatment that are described in the protocol-related documents, such as the IRB-approved

research protocol, the informed consent document, and IB; and (b) the characteristics of the participant population being studied.

2. Related or possibly related to participation in the research (“possibly related” means there is a reasonable possibility that the incident, experience, or outcome may have been caused by the procedures/treatment involved in the research); and
3. Suggests that the research places participants or others at a greater risk of harm (including physical, psychological, economic, or social harm) than was previously known or recognized.
4. Please reference the UNC Office for Human Research Ethics SOP 1401 to address Promptly Reportable Information. This SOP provides definitions and procedures for the reporting promptly reportable information to the UNC-Chapel Hill IRB.

9.8 NSI Reporting

The investigator will report NSI to the UNC IRB. The NSI report will include the following information:

1. Protocol identifying information: protocol title and number, PI’s name, and the IRB project number.
2. A detailed description of the event, incident, experience, or outcome.
3. An explanation of the basis for determining that the event, incident, experience, or outcome represents an NSI;
4. A description of any changes to the protocol or other corrective actions that have been taken or are proposed in response to the NSI.

To satisfy the requirement for prompt reporting, NSI reports will be reported using the following timeline:

1. NSI that are SAEs will be reported to the IRB and the DAIDS MO within 3 business days of the investigator becoming aware of the event.
2. Any other NSI will be reported to the IRB and to the DAIDS MO within 7 business days of the investigator becoming aware of the event.
3. All NSI should be reported to appropriate institutional officials (as required by an institution’s written reporting procedures), the NIH MO (or designee), and the OHRP within 30 business days of the IRB’s review and determination that the report of the problem from the investigator imposed a safety risk.

9.9 Reporting NSI to Participants

We would inform all study participants by letter or electronic messaging of any NSI if it is determined by the UNC IRB to merit such notice.

10 STATISTICAL CONSIDERATIONS

10.1 Statistical Hypotheses

1. Vaccination with either C62-M4 or C1C62-M3M4 will be safe and well tolerated
2. Both C62-M4 and C1C62-M3M4 vaccination will increase the frequency of circulating HIV-specific T cells
3. C1C62-M3M4 will induce a greater breadth of T cells targeting conserved regions of HIV than C62-M4

10.3 Sample Size Determination

The proposed number of 8 vaccinees per arm and 2 placebo controls was determined to be sufficient to evaluate the risk of common SAEs or severe local or systemic reactions based on

early phase trials of simian adenovirus- and MVA-vectored vaccines, given alone or serially (59, 64, 92-94, 97, 121, 125-128, 136-139).

Enrollment into the trial will be suspended if two or more participants experience a study treatment-related AE of Grade 3 or higher or if one or more participants experience an SAE possibly related to study treatment.

If zero of 8 participants experience a safety event, an exact one-sided binomial 95% upper confidence limit for the probability of a safety event will be 31%. If one participant experiences a safety event, the corresponding one-sided 95% upper confidence limit will be 47%. If no safety events are observed in the two vaccine arms and data is pooled across arms (n=16), then the exact one-sided 95% upper confidence limit will be 17%.

10.4 Procedure for missing and invalid data

There is very little missing or invalid data in our concurrent study using MVA-vectored vaccines (NCT03844386; IND 18368), so it is anticipated that this study will be similar. Due to the small sample size, formal imputation methods will not be used. However, if there is concern that key findings are sensitive to missing data, missing values can be replaced with the best (worst) rank in the **C62-M4** arm and the worst (best) rank in the **C1C62-M3M4** arm to determine if findings are sensitive to missingness.

Safety analyses will include all evaluable participants regardless of whether they are replaced or missing for additional endpoints. In order to achieve the planned evaluable sample size, participants who do not receive both sets of vaccines at D0 and D28 will be replaced.

10.5 Study Duration and Accrual

Participants will be screened approximately 60 days prior to vaccination and will be followed for 196 days after vaccination. The total study duration from screening to completion of follow-up per participant will be approximately 36 weeks (approximately 9 months). Given the focus of this study is on safety and potential adverse events, accrual will be staggered such that a maximum of up to 2 participants per week will receive the Day 0 vaccination.

10.6 Randomization

Following enrollment, the 18 study participants will be randomly assigned to receive vaccination with either **C62-M4** (n=8), **C1C62-M3M4** (n=8), or placebo (n=2) through a double-blinded, randomized block design. As detailed in (Section 7.2.1), participants who do not receive both sets of vaccines at D0 and D28 will be replaced. In cases such as these, the unblinded statistician will generate a new randomization ID that will serve as a replacement for the investigational product assigned to the dropout.

10.7 Statistical Analyses

10.7.1 General Approach

This is a Phase 1 study with a small sample size chosen to evaluate safety and the primary efficacy outcome. Exact methods that do not rely on large sample assumptions will be used for statistical inference and presented with descriptive statistics and/or data visualization. When feasible, graphs will present data at the participant-level with summary statistics. Emphasis will be placed on descriptive summaries and estimated effect sizes.

For inferential tests, a significance level of 0.05 will be employed. However, this study recruits a small number of participants and thus may not detect scientifically meaningful effects at a significance level of 0.05. Since this is a small study with multiple exploratory endpoints, adjustment for multiple hypothesis testing will not be performed. Results should be interpreted within the context of the protocol-defined eligibility criteria and the target population available and willing to participate in this double-blinded, placebo-controlled, randomized clinical trial.

10.7.2 Analysis of the Primary Safety Endpoint(s)

The probability of a primary safety event (\geq Grade 3 AE) from D0 through D56 (or 28 days following the second vaccination) will be estimated with a proportion and corresponding one-sided exact binomial 95% upper confidence limit. These estimates will be calculated separately for **C62** (D0) followed by **M4** (D28) and **C1C62** (D0) followed by **M3M4** (D28) in PWH on ART.

NOTE: The occurrence of a Grade 3 elevated blood pressure during a study-related leukapheresis that resolves following completion of the procedure will not be included as a primary safety endpoint.

10.7.3 Analysis of the Secondary Safety Endpoints

The probability of a secondary safety event (\geq Grade 1 AE) from D0 through D196 will be estimated with a proportion and corresponding one-sided exact binomial 95% upper confidence limit. These estimates will be calculated separately for **C62** (D0) followed by **M4** (D28) and **C1C62** (D0) followed by **M3M4** (D28) in PWH on ART.

NOTE: Safety events include incidence and grade of all reportable unsolicited and solicited adverse events including SAEs, MAAEs, and AESIs post first dose of C1 and/or C62 through Day 196.

10.7.4 Analysis of Secondary Immunogenicity Endpoints

10.7.4.1 T cell magnitude

To evaluate changes in HIV-1 epitope-specific CD8⁺ T cell responses detected in IFN- γ ELISpot assays from baseline (pre-vaccination) to post-boost vaccination (D35 and D42), the relative change within participants will be estimated using a geometric mean ratio (GMR, also known as fold change) and evaluated with an exact two-sided Wilcoxon signed-rank test for within-arm comparisons and an exact two-sided Wilcoxon rank-sum test for between-arm comparisons. The Wilcoxon signed-rank test assumes symmetry of the change in natural log-transformed summed HIV-1 specific T cell response (estimated by GMR) under the null. If this assumption is violated, then a sign test will be conducted as a sensitivity analysis.

10.7.4.2 Power Calculations

To compute power for a continuous covariate, such as T cell magnitude, a meaningful effect size must be determined ahead of time. Comparing T-cell responses within participants, an average fold change of at least 2 (GMR \geq 2) is anticipated to be scientifically meaningful. Baseline HIV-specific T cell responses from HIV-infected durably-suppressed PWH (53) were used to inform power calculations. A between-participant standard deviation of 0.8 was estimated using this data and the same standard deviation is assumed pre- and post-vaccination.

Assuming the natural, log-transformed, HIV-specific T cell responses follow a normal distribution with between-participant standard deviation of 0.8 and a within-participant Pearson correlation of 0.9 for pre- and post-vaccine measurements, using 10,000 simulated datasets for n=8 participants provides 87% power to detect a GMR of 2 or greater. For a smaller within-participant correlation of 0.8, there is >95% power to detect a GMR of 2 or greater.

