Design: Empirical power calculated by simulating 10,000 random samples, assuming log-transformed HIV-specific T-cell response follows a normal distribution. The effect under the alternative hypothesis was a GMR of 2 on the raw T-cell response measures. An SD of 0.8 for both pre- and post-vaccination measurements was assumed to calculate power. This assumption was based on previous, log-transformed HIV-specific T-cell response data, which gave a between-participant SD of 0.8 at baseline. A within-participant Pearson correlation of between r = 0.8 and r = 0.9 was assumed between paired log-transformed HIV-specific T-cell response measures.

Design: Empirical power calculated by simulating 10,000 random samples from a normal distribution. Assume a p=90% or p=87% probability that the difference in HIV-specific T-cell response for any given participant in the **C1C62-M3M4** arm is higher than any given individual in the **C62-M4** arm.

Statistical Test for Power: Two-Sided Exact Wilcoxon Signed-Rank Test to achieve exact p-value < 0.05

Statistical Test for Power: Two-Sided Exact Wilcoxon Rank-Sum Test to achieve exact p-value < 0.05

| Sample Size: N=8 (per arm) | Sample Size: N=8 (per arm) |
|----------------------------------|----------------------------|
| Empirical Power: | Empirical Power: |
| >95% (within-individual r = 0.9) | 90% (p=90% effect size) |
| >80% (within-individual r = 0.8) | >80% (p=87% effect size) |

Table 5: Power for detecting differences in T-cell breadth between arms.

Aim: Determine the statistical power necessary to detect a change in T-cell breadth (T cell breadth is defined as the number of reactive HIV subpools as described in Section 8.2) between vaccine arms

Data: For the C62-M4 and C1C62-M3M4 arms, we anticipate that vaccination will induce a change of breadth (the detection of a new reactive T cell epitope) ranging from 0-3 epitopes and 2-6 epitopes, respectively. We anticipate that C62-M4 will induce a change in breadth with the following frequency distribution: 0 (20% of participants), 1 (50%), 2 (20%), and 3 (10%). We anticipate that C1C62-M3M4 will induce a change in breadth with the following frequency distribution: 2 (30% of participants), 3 (40%), 4 (15%), 5 (10%), and 6 (5%). Note, that these estimates are based on previous empirical

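### Protocol 10.7.4.2 attaches its two within-arm power figures to the wrong correlations: its own assumptions give about 99% at 0.9 and 87% at 0.8

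*Protocol*

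**What the plan says.** Protocol 10.7.4.2 gives the only power statement in the protocol for the within-arm magnitude endpoint, which is a secondary endpoint. Its model is set out as "Assuming the natural, log-transformed, HIV-specific T cell responses follow a normal distribution", and on variability it says: "A between-participant standard deviation of 0.8 was estimated using this data and the same standard deviation is assumed pre- and post-vaccination". The effect is a geometric mean ratio (GMR) of 2, with 8 participants per arm and 10,000 simulated datasets. At a pre-post correlation of 0.9, it says, this "provides 87% power to detect a GMR of 2 or greater. For a smaller within-participant correlation of 0.8, there is >95% power to detect" the same effect.

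Protocol 10.7.4.1 says the change will be "evaluated with an exact two-sided Wilcoxon signed-rank test for within-arm comparisons". Protocol 10.7.1 sets the level: "For inferential tests, a significance level of 0.05 will be employed".

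SAP 5.3, Table 4, describes the same calculation, with the same SD, GMR, n, test and number of simulations. Its results are ">95% (within-individual r = 0.9") and ">80% (within-individual r = 0.8").

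**The concern.** In a paired design, the correlation between the two measurements is what removes between-participant variation. The lower it is, the noisier the paired difference and the lower the power, if everything else stays the same. The protocol reports the reverse, and it calls 0.8 the smaller correlation in the same sentence, so this is not a misreading of which case is which. The SAP reports the opposite order from identical inputs, so at least one document must be wrong.

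Two things are at stake. The protocol overstates power at the less favourable of its two correlations. It also gives the wrong sensitivity message, because it presents weaker correlation as the safer case. Someone interpreting a null within-arm result from 8 participants would be misled about how informative it is.

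**Working it through.** **Inputs**

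- SD of the natural-log response: 0.8 before and after vaccination (Protocol 10.7.4.2; SAP Table 4)
- Effect: GMR 2, so the mean paired difference is ln 2 = 0.693
- n = 8 per arm
- Test: exact two-sided Wilcoxon signed-rank (Protocol 10.7.4.1; SAP Table 4)
- Alpha: 0.05 (Protocol 10.7.1)
- Correlation r: 0.9 and 0.8

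**Step 1: SD of the paired difference.** With equal SDs, SD(diff) = 0.8 × √(2(1 − r)).

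- r = 0.9: 0.8 × √0.2 = 0.358, so the standardised effect is 0.693 / 0.358 = 1.94
- r = 0.8: 0.8 × √0.4 = 0.506, so the standardised effect is 0.693 / 0.506 = 1.37

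The effect in SD units is smaller at 0.8, so power must be lower there. This settles the order without simulation.

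**Step 2: rejection region.** With n = 8 there are 2^8 = 256 equally likely sign patterns under the null. A smaller rank sum of 3 or less has exact two-sided p = 10/256 = 0.039. Allowing 4 gives 14/256 = 0.055, which exceeds 0.05. The test therefore rejects at 3 or less.

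**Step 3: power.** Paired differences were drawn as Normal(ln 2, SD(diff)), with 400,000 datasets per case. The case was also run five times with 10,000 bivariate-normal datasets, which is the scheme the protocol describes.

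| r | SD(diff) | Power, 400,000 datasets | Range over five runs of 10,000 | Protocol | SAP |
|---|---|---|---|---|---|
| 0.9 | 0.358 | 99.0% | 98.9% to 99.1% | 87% | >95% |
| 0.8 | 0.506 | 86.6% | 86.3% to 86.7% | >95% | >80% |

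The protocol's figure is not reproduced at the correlation it names: 99.0% against 87%, a gap of 12 points. It is reproduced at r = 0.8, where 86.6% rounds to 87%. The figure of over 95% is true at r = 0.9. Both SAP entries are true.

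**Step 4: could another reading give the printed order?**

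| Variant | r = 0.9 | r = 0.8 |
|---|---|---|
| One-sided signed-rank | 99.8% | 94.2% |
| Paired t | 99.6% | 91.1% |
| Normal approximation | >99.9% | 97.2% |
| Sign test | 80.7% | 49.1% |
| Shift of 1 (log2 scale), SD 0.8 | 100% | 99.2% |
| Shift of log10(2), SD 0.8 | 46.8% | 25.7% |
| n = 7, two-sided signed-rank | 97.8% | 82.0% |
| n = 6, two-sided signed-rank | 85.2% | 58.5% |

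Power falls from 0.9 to 0.8 in every row. No variant yields 87% at 0.9 together with more than 95% at 0.8.

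**Step 5: below the planned range (illustrative).** The same calculation gives 71% at r = 0.7 and 49% at r = 0.5. The documents do not assume correlations this low. The figures only show how fast power falls in the direction that the protocol presents as favourable.

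**The case against.** The best case for leaving this alone is that nothing in the design depends on it. Sample size is justified on safety (Protocol 10.3, SAP 5.1). Protocol 10.7.1 already warns that the study may miss meaningful effects at the 0.05 level and puts the emphasis on description and effect sizes. Magnitude is a secondary endpoint, and n = 8 still gives about 87% or more at both planned correlations. The SAP has the right order, so a careful reader could resolve the conflict. All of that stands, and it limits the consequence, but it does not make the protocol's statement true.

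Three narrower objections also have force:

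- The SAP's entry of over 80% at r = 0.8 is correct as it is. Changing it to 87% would only be harmonisation.
- The results at 0.7 and 0.5 lie outside the 0.8 to 0.9 that the SAP assumes, and Protocol 4.2 describes these responses as highly stable in this population. They are illustration, not evidence of low power in this trial.
- The SAP averages the baseline visits (sections 4.2 and 8.2), whereas the power model uses one pre and one post value. The correlation that applies to the analysed contrast may therefore differ from the modelled one. That affects the absolute power in practice, but it cannot reverse the order under the stated model.

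The discrepancy is not a matter of superseded text. The SAP is written for Protocol version 3.0, and the January 2024 clarification memo does not touch 10.7.4.2.

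**Conclusion.** The error is confirmed with high confidence. At a correlation of 0.8 the protocol claims over 95% power where its own assumptions give 87%. The chance of missing a true doubling is then about 13% (100 − 86.6 = 13.4), not under 5%. At 0.9 the protocol understates power by 12 points. Only the protocol is wrong.

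The recalculated values rest on the plan's own model: normal log responses, SD 0.8 at both times, a true GMR of exactly 2, 8 evaluable participants and the exact two-sided signed-rank test. The conclusion about order needs less, only that SD, n, effect and test are the same in both cases. This is a reporting error that should be corrected. It does not affect the sample size, the primary safety endpoint or the planned analysis.

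**What to change.** In Protocol 10.7.4.2, restate the result as: power above 95% (about 99%) at a within-participant correlation of 0.9, and 87% at 0.8. This brings the protocol into line with SAP Table 4. Optionally, give 87% in place of the lower bound for r = 0.8 in SAP Table 4, so that both documents show the same number.

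The cost is one sentence in a clarification memo, a route the sponsor has already used for this protocol version. Design, conduct and analysis do not change.
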